## **10.4 Informed consent**

The Principal Investigator(s) at each study center will:

- Ensure each patient or legal guardian is given full and adequate oral and written information about the nature, purpose, possible risk and benefit of the study (before

any study procedures are performed) as per local requirements. The ICF needs to be adjusted as per local requirements.

- Ensure each patient or legal guardian is notified that they are free to discontinue from the study at any time.
- Ensure that each patient or legal guardian is given the opportunity to ask questions and allowed time to consider the information provided.
- Ensure each patient or legal guardian provides signed and dated Informed Consent before conducting any procedure specifically for the study.
- Ensure the original, signed Informed Consent(s) is/are stored in the Investigator's Study File and kept for a period that is compliant with GCP/local regulatory requirements, whichever is longer.
- Ensure a copy of the signed Informed Consent Form is given to the patient.
- Ensure that any incentives for patients who participate in the study as well as any provisions for patients harmed as a consequence of study participation are described in the Informed Consent Form that is approved by an Ethics Committee.

## **10.5 Changes to the protocol and informed consent form**

Study procedures will not be changed without the mutual agreement of the International Coordinating Investigator and AstraZeneca.

If there are any substantial changes to the study protocol, then these changes will be documented in a study protocol amendment and where required in a new version of the study protocol (Revised CSP).

The amendment is to be approved by the relevant EC and if applicable, also the national regulatory authority approval, before implementation. Local requirements are to be followed for revised protocols.

AstraZeneca will distribute any subsequent amendments and new versions of the protocol to each Principal Investigator(s). For distribution to EC see Section 10.3.

If a protocol amendment requires a change to a study center's ICF, AstraZeneca and the study center's EC are to approve the revised ICF before the revised form is used.

If local regulations require, any administrative change will be communicated to or approved by each EC.

## **10.6 Audits and inspections**

Authorised representatives of AstraZeneca, a regulatory authority, or an EC may perform audits or inspections at the study center, including source data verification. The purpose of an audit or inspection is to systematically and independently examine all study-related activities and documents, to determine whether these activities were conducted, and data were recorded,

Clinical Study Protocol  
Drug Substance Benralizumab (Medi-563)  
Study Code D3250C00031  
Version 1.0  
Date 23 August 2016

analysed, and accurately reported according to the protocol, GCP guidelines of the International Conference on Harmonisation (ICH), and any applicable regulatory requirements. The Investigator will contact AstraZeneca immediately if contacted by a regulatory agency or other body about an inspection or an audit at the study center.

---

## LIST OF ABBREVIATIONS

Abbreviation or special term	Explanation
ACQ-6	Asthma Control Questionnaire-6
ADA	Anti-drug antibodies
AE	Adverse event
AI	Auto-Injector
ALT	Alanine aminotransferase
AST	Aspartate aminotransferase
ATC	Anatomical therapeutic chemical
AZDD	AstraZeneca drug dictionary
BMI	Body mass index
CSP	Clinical study protocol
CSR	Clinical Study report
DAE	AEs causing discontinuation of investigational product
ECG	Electrocardiogram
eCRF	Electronic case report form
EOT	End-of-treatment
FAS	Full analysis set
FEV1	Forced expiratory volume in 1 second
FSH	Follicle-stimulating hormone
FVC	Forced vital capacity
GGT	Gamma-glutamyl transpeptidase
HIV	Human immunodeficiency virus
ICS	Inhaled corticosteroids
IFU	Instructions for Use
IP	Investigational product
IPD	Premature IP Discontinuation
MedDRA	Medical Dictionary for Regulatory Activities
nAb	Neutralizing antibody
N/A	Not applicable
OCS	Oral corticosteroids

Abbreviation or special term	Explanation
PI	Principal investigator
PK	Pharmacokinetic(s)
Post-BD	Post-bronchodilator
PT	Preferred term
SAE	Serious adverse event
SAS	SAS Institute Inc., Cary, NC
SC	Subcutaneous
SD	Standard deviation
SI	International System of Units
SOC	System organ class
TBL	Total bilirubin
TIA	Transient ischemic attack
ULN	Upper limit of normal
Unsch	Unscheduled
WBDC	Web Based Data Capture
WOCBP	Women of childbearing potential

## AMENDMENT HISTORY

---

Date	Brief description of change
9/25/2017	

1. The study is reported using the AstraZeneca drug dictionary (AZDD) instead of pre-specified WHO drug dictionary (WHODD) because the timeline for transition to the WHODD was delayed.

2. Visit Window adjusted to protocol schedule at assessment item level (See Section 2.2.2)

3. Added Section 6 Change of analysis from protocol for the analysis of physical examination data

---

## 1. STUDY DETAILS

### 1.1 Study objectives

#### 1.1.1 Primary Objective

Objective	Outcome measure
To assess patient- or caregiver-reported functionality and reliability of the benralizumab single-use auto-injector (AI) in an at-home setting and performance of the AI device after use.	
 
• Proportion of patients/caregivers who successfully administered benralizumab 30 mg subcutaneously (SC) by injection with an AI device at home
 
• Proportion of returned AI devices used to administer benralizumab at home that have been evaluated as functional
 
• Proportion of AI devices used to administer benralizumab at home or in the clinic and have been reported as malfunctioning (Product Complaints)
 

#### 1.1.2 Secondary Objectives

Objective	Outcome measure
To monitor metrics of asthma control	
 
• Change from baseline in mean Asthma Control Questionnaire-6 (ACQ-6) score
 

To evaluate the pharmacokinetics, pharmacodynamics, and immunogenicity of benralizumab	
 
• Pharmacokinetic parameters
 
• Peripheral blood eosinophil levels
 
• Anti-drug antibodies (ADA)
 

#### 1.1.3 Safety Objective

Safety objectives	Outcome measure
To assess the safety and tolerability of benralizumab	
 
• Adverse events (AEs) and serious adverse events (SAEs)
 
• Laboratory variables
 
• Physical examination
 

This statistical analysis plan (SAP) outlines the analyses to be generated for the global clinical study report (CSR). Additional analyses required for regional submissions (if applicable) will be pre-specified in a separate analysis plan and will be submitted to the appropriate authorities.

## **1.2 Study design**

This is an open-label study designed to assess patient- or caregiver-reported functionality, performance, and reliability of an AI with a fixed 30 mg dose of benralizumab administered SC in an at-home setting.

Approximately 120 patients, 18 to 75 years of age, globally with severe asthma will enter the treatment period to receive 5 SC doses (Week 0, Week 4, Week 8, Week 12, and Week 16) of benralizumab.

Following a 2-week screening period, eligible patients will receive 3 SC doses of 30 mg of benralizumab at the study site (Week 0, Week 4, and Week 8). At Week 0, the Principal Investigator (PI) or his/her designee will administer the study drug. At Week 4, the patient or caregiver will have the option of administering the study drug under site supervision to ensure they understand the procedure and are capable of doing so. At Week 8, the patient or caregiver will have to perform the injection, again under site staff supervision. Patients or caregivers unable or unwilling to administer investigational product (IP) at this visit will be discontinued from the study.

The patient or caregiver will be given the Instructions for Use (IFU) to refer to for home administrations. The final 2 doses of benralizumab (Week 12 and Week 16) will be self-administered by the patient or administered by the caregiver at home. After each of these administrations, the patient will return for a scheduled on-site visit within 48 hours.

For the at-home administrations, whether the patient is self-administering or the caregiver is administering to a patient, that person administering the dose will fill out a questionnaire designed to indicate whether the device functioned correctly and the dose was successfully administered. Both the completed questionnaire and the used device are to be returned to the site during each of the clinic visits (Visit 5 [Week 12] and Visit 6 [Week 16]). The site is to subsequently return the used devices and questionnaires to the Sponsor for evaluation.

An end-of-treatment (EOT) visit will be performed at Week 20 and a follow-up visit at Week 28 (12 weeks after last IP administration).

## **1.3 Number of subjects**

Approximately 120 patients will receive treatment to allow approximately 100 patients to complete the study. It is based upon a targeted recruitment with an adjustment to account for a 17% patient drop-out rate.

## **2. ANALYSIS SETS**

### **2.1 Definition of analysis sets**

Three patient populations are defined below: All patients analysis set, Full analysis set (FAS), and Pharmacokinetics analysis set.

Patients must have provided their informed consent. If no signed informed consent is collected (major protocol deviation [PD]), then the patient will be excluded from all analysis sets defined below.

#### **2.1.1 All patients analysis set**

The all patients analysis set will comprise all patients screened for the study, ie, signed informed consent form, and will be used for reporting of disposition and screening failures.

#### **2.1.2 Full analysis set**

All patients receiving any IP will be included in the full analysis set (FAS), irrespective of their protocol adherence and continued participation in the study. Patients who withdraw consent to participate in the study will be included up to the date of their study termination.

All analyses, except for PK analysis, will be presented using the FAS.

#### **2.1.3 Pharmacokinetic analysis set**

All patients who received benralizumab and from whom PK blood samples were obtained are assumed not to be affected by factors such as protocol violations will be included in the PK analysis dataset. Those patients who had at least 1 quantifiable serum PK observation post first dose will be included in the PK analysis dataset. All PK summaries will be based on this analysis set.

### **2.2 Violations and deviations**

Patients who do not meet eligibility criteria but are still enrolled will be analyzed according to the analysis sets described in [Section 2.1](#). There is no intention to perform a per-protocol analysis in this study.

#### **2.2.1 Important protocol deviations**

Important deviations will be those which are considered to potentially impact upon the interpretation of the primary endpoint in the study. Only important protocol deviations will be listed and tabulated in the CSR.

The following categories of protocol deviations will be reviewed by medical advisors and statisticians prior to database lock to determine those which are considered important deviations as outlined above.

- Patients who do not meet the inclusion criteria
- Patients who meet any of the exclusion criteria
- Concomitant use of disallowed medications (to be identified through programming)
- Patients who developed withdrawal criteria during the study but were not withdrawn

Patients for whom a significant protocol deviation was recorded that impacts the interpretation of the study safety outcomes will have a footnote added to applicable output to describe the deviation and its potential impact. Such patients will be identified as part of the protocol deviation review process, prior to database lock.

### 2.2.2 Visit window definitions

The adjusted analysis-defined windows will be based on the collection schedule listed in the protocol and variables will be windowed to the closest scheduled visit for that variable.

No windows will be applied for the screening visit. For endpoints that present visit-based data, the variables will be summarized based on the scheduled days with adjusted analysis-defined visit windows. The adjusted analysis-defined windows will be based on the collection schedule listed in the protocol and variables will be windowed to the closest scheduled visit for that variable. Visit windows have been constructed so that every observation collected can be allocated to a particular visit. The adjusted analysis-defined windows are summarized in **Error! Reference source not found.a-1c**.

**Table 1a** Visit windows for assessments [ACQ-6]

Defined Windows Visit	Scheduled Study Day	Maximum Windows
Week 0 Day 1	1	Study Day=1
Week 4	29	$2 \leq \text{Study Days} \leq 42$
Week 8	57	$43 \leq \text{Study Days} \leq 70$
Week 12	85	$71 \leq \text{Study Days} \leq 98$
Week 16	113	$99 \leq \text{Study Days} \leq 126$
Week 20	141	$127 \leq \text{Study Days}$

**Table 2b** Visit windows for assessments [Laboratory tests - Chemistry, Haematology, Urinalysis]

Defined Windows Visit	Scheduled Study Day	Maximum Windows
Week 0 Day 1	1	Study Day=1
Week 20	141	$2 \leq \text{Study Days} \leq 154$
Week 28	197	$155 \leq \text{Study Days}$

**Table 3c** Visit windows for assessments [PK and ADA]

Defined Windows Visit	Scheduled Study Day	Maximum Windows
Week 0 Day 1*	1	Study Day=1
Week 8*	57	$2 \leq \text{Study Days} \leq 98$
Week 20	141	$99 \leq \text{Study Days} \leq 154$
Week 28	197	$155 \leq \text{Study Days}$

\* Only take pre-dose. For PK assessments, visit window is only applicable to unscheduled visits.

For assignment of data to adjusted analysis-defined visit windows, study day will be defined as follows:

$$(\text{Date of assessment} - \text{date of first dose}) + 1$$

If multiple readings are recorded within a single adjusted visit window, please refer to the rules below.

- If there are 2 or more valid, non-missing observations within the same visit window, then the non-missing one closest to the scheduled visit will be used in the analysis.
- If 2 valid observations are equidistant from the scheduled visit, then the non-missing observation with the earlier collection date will be used in the analysis.
- If 2 or more valid observations are collected on the same day, then the non-missing observation with the earlier collection time will be included in the analysis.

If a visit window does not contain any observations, then the data will remain missing.

All data will be organized and analyzed according to the scheduled visits outlined in the protocol. However, actual observation visit times may differ from the scheduled visit times and where this occurs the results should be allocated to the most appropriate visit. Time

intervals (eg, adjusted visit windows) have been constructed so that every observation collected can be allocated to a particular visit.

Any repeat or additional assessments performed will be included in the individual patient data listings.

For all vital signs, the visit recorded in Web Based Data Capture (WBDC) will be used.

For the central laboratory results and other endpoints that present visit-based data (ADA/nAb, ACQ-6), the variables will be summarized based on the scheduled days with adjusted analysis-defined visit windows.

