### **3.6 Discontinuation of investigational product**

Patients will be discontinued from IP in the following situations:

1. Patient decision. The patient is free to discontinue treatment at any time without prejudice to further treatment.
2. Adverse event (AE) that, in the opinion of the Investigator, contraindicates further dosing
3. Risk to patient as judged by the Investigator or AstraZeneca
4. Severe non-compliance to study protocol
5. Eligibility requirement found not to be fulfilled (see Section 3.4)
6. Pregnancy
7. Lost to follow-up
8. Development of any study specific criteria for discontinuation:
  1. Anaphylactic reaction to the IP requiring administration of epinephrine
  2. Development of helminth parasitic infestations requiring hospitalization
  3. An asthma-related event requiring mechanical ventilation.
9. A patient who is self-administering IP who becomes unwilling or unable to continue to self-administer must be discontinued. Similarly, if a caregiver is giving the IP and becomes unwilling or unable to continue to administer IP to a patient, then that patient must be discontinued.

All patients who prematurely discontinue IP should return to the study center and complete the procedures described for the Premature IP Discontinuation (IPD) visit after 4 weeks ( $\pm 3$  days) and

---

 Patient is considered lost to follow up when any of the following attempts of contact are failed: -3 attempts of either phone calls, faxes or emails; - having sent 1 registered letter/certified mail; 1 unsuccessful effort to check the vital status of the patient using publicly available sources, if allowed by local regulations.

the procedures for the Follow-up visit after 12 weeks ( $\pm 3$ days) of the last IP administration. The reason(s) for premature discontinuation of IP should be recorded in the eCRF.

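### The SAP's laboratory windows have no IPD row and count from the first dose, so after a last dose at Week 0 or 4 the Follow-up value is shown as Week 20 and the IPD value leaves the by-visit summary

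*SAP*

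**What the plan says.** Protocol 3.6 asks patients who stop treatment early to attend an IPD visit 4 weeks (±3 days) after the last administration, and "the procedures for the Follow-up visit after 12 weeks" (±3 days) from that same administration.

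SAP 2.2.2 defines study day from the date of the first dose, which is Day 1. Its laboratory table (listed as Table 1b, captioned 2b in the section) has three rows: Week 0 (Day 1), Week 20 (scheduled Day 141, window Days 2 to 154) and Week 28 (scheduled Day 197, window Day 155 onward). No row is given for IPD. If a window contains two or more valid values, "then the non-missing one closest to the scheduled visit will be used in the analysis". The section also states: "Visit windows have been constructed so that every observation collected can be allocated to a particular visit".

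The windows are applied explicitly: "For the central laboratory results and other endpoints that present visit-based data (ADA/nAb, ACQ-6), the variables will be summarized based on the scheduled days" and the adjusted windows. Two data types are treated differently. For vital signs the rule is "For all vital signs, the visit recorded in Web Based Data Capture (WBDC) will be used". The footnote to the PK and ADA table (Table 1c, captioned 3c) reads "Only take pre-dose. For PK assessments, visit window is only applicable to unscheduled visits".

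SAP 3.2.2 places eosinophil sampling at screening, Week 0, EOT/IPD and Follow-up. SAP 3.4 and 3.5 place ADA sampling on a schedule similar to PK, which includes IPD and Follow-up. SAP 4.2.9.2, 4.2.10.3 and 4.2.12 summarize eosinophils, laboratory variables and ADA/nAb by visit or time point.

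**The concern.** The visits of an early stopper are timed from the last dose, but the windows run from the first. A patient who stops early enough has both the IPD and the Follow-up sample inside the single Week 20 laboratory window, and only one of them can be used. The rule picks the later one because it is nearer Day 141.

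For such a patient the Week 20 entry is then a value taken 84 days after the last dose, pooled with completers whose Week 20 value is taken 28 days after theirs (Day 141 − Day 113). The patient's own 28-day value is not summarized by visit. Eosinophils and ADA are secondary outcomes and laboratory variables are safety outcomes, so the row labels should mean what they say.

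**Working it through.** **Inputs.** Doses at Weeks 0, 4, 8, 12 and 16 (SAP 1.2). IPD at last dose + 28 days and Follow-up at last dose + 84 days, each ±3 days (Protocol 3.6). Dosing visits ±3 days (Protocol Table 2). Windows and selection rule from SAP 2.2.2.

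**The plan's own figures.** Scheduled day = 7 × week + 1. Week 20: 7 × 20 + 1 = 141. Week 28: 7 × 28 + 1 = 197. Both match Table 1b. For a completer, 113 + 28 = 141 and 113 + 84 = 197, so the table fits completers exactly.

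**Early stoppers, both visits attended.** With last-dose day L = 7 × week + 1, IPD = L + 28 and Follow-up = L + 84. Ranges in brackets let the last dose, IPD and Follow-up each move by ±3 days (the Week 0 dose is fixed at Day 1).

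| Last dose | L | IPD day | IPD distance from 141 | Follow-up day | Follow-up distance from 141 | Used as Week 20 | Used as Week 28 |
|---|---|---|---|---|---|---|---|
| Week 0 | 1 | 29 (26–32) | 112 (109–115) | 85 (82–88) | 56 (53–59) | Follow-up | none |
| Week 4 | 29 | 57 (51–63) | 84 (78–90) | 113 (107–119) | 28 (22–34) | Follow-up | none |
| Week 8 | 57 | 85 (79–91) | 56 (50–62) | 141 (135–147) | 0 (0–6) | Follow-up | none |
| Week 12 | 85 | 113 (107–119) | 28 (22–34) | 169 (163–175) | outside window | IPD | Follow-up |

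In the first three rows the smallest possible IPD distance exceeds the largest possible Follow-up distance (109 > 59, 78 > 34, 50 > 6). The result therefore does not depend on where in the visit windows the patient falls. Enumerating the shifts confirms it: Follow-up is used in 49 of 49 combinations for Week 0 (7 × 7) and in 343 of 343 for each of Weeks 4 and 8 (7 × 7 × 7).

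**Reading the rows.**
- Week 0 or 4: the Week 20 label is 56 or 28 days off, and the IPD value is omitted.
- Week 8: the label agrees with the calendar, and only the IPD value is omitted.
- Week 12: nothing is displaced, but IPD on Day 113 is labelled Week 20, and Follow-up on Day 169 is labelled Week 28 (197 − 169 = 28 days early).

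**ADA/nAb (Table 1c).** Here Week 8 covers Days 2–98 and Week 20 covers Days 99–154. After a last dose at Week 4, Follow-up on Day 113 is shown as Week 20, 28 days early. After a last dose at Week 8, Follow-up on Day 141 is correctly placed. IPD after Week 0, 4 or 8 (Days 29, 57, 85) and Follow-up after Week 0 (Day 85) fall in Days 2–98. The footnote limits that row to pre-dose samples and these samples precede no dose, so how they are handled cannot be determined.

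**How many patients.** The documents do not say. As an assumption only: if all 120 treated patients had a Week 20 laboratory value, 1, 5, 10 or 20 affected patients would make up 0.8%, 4.2%, 8.3% or 16.7% of them. None of these is a bound.

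**The case against.** Calendar-time windowing is a legitimate choice and it is the stated one. Protocol 8.5 uses secondary data regardless of whether treatment was stopped, and under that approach taking the value nearest Day 141 is intended. This stands for a last dose at Week 8. It does not carry over to Weeks 0 and 4: a window opening on Day 2 lets a Day 85 value stand for Day 141.

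SAP 3.3 says safety measurements use all available data, and 2.2.2 speaks of allocating results to the most appropriate visit. Both are general statements. Neither supplies an IPD rule or displaces the explicit one-value-per-window rule for by-visit summaries. They do fit the maximum/minimum displays, which keep the IPD value.

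A reader might also infer that the windows contradict SAP 3.2.2. That goes too far: 3.2.2 is a sampling schedule, writes EOT/IPD as one slot, and does not define analysis rows. Nor is the empty Week 28 cell an error in itself, since after a last dose at Week 0, 4 or 8 no scheduled sample lies near Day 197.

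Finally, the study is single-arm and descriptive with no hypothesis tests, which limits how much the point can matter. That stands.

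**Conclusion.** The point holds, as a minor one. Under the SAP's own rules, a patient who attends both visits after a last dose at Week 0 or 4 has the Follow-up laboratory value reported as Week 20 (56 or 28 days early at the nominal dates), and the IPD value is left out of the by-visit summary. After Week 8 only the omission remains. After Week 12 only the label shift remains. For ADA/nAb the clear label error is the Week 4 case.

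IPD sampling is stated in the text for haematology (hence eosinophils) and, through the PK schedule, for ADA. For chemistry and urinalysis it is inferred, because those schedule rows are not legible in the text available.

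Only the by-visit descriptive summaries are touched. Primary endpoints, scheduled PK samples, maximum/minimum shift tables, liver displays, ADA at any time and listings are not. A reader might infer that the eosinophil results would be biased. The documents give no eosinophil recovery time and no count of affected patients, so no size or direction of distortion can be claimed.

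**What to change.** In SAP 2.2.2:

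- Assign scheduled central laboratory and ADA/nAb samples to the visit recorded in WBDC, as is already done for vital signs, with IPD as its own row.
- Present early stoppers' Follow-up separately from the completers' Week 28, or footnote it as 12 weeks after the last dose. Its calendar time and dose count differ too: Day 85, 113, 141 or 169 after a last dose at Week 0, 4, 8 or 12, against Day 197. Pooling the two would replace one mislabelled row with another.
- Use day windows for unscheduled samples only, and start the laboratory Week 20 window near Week 20, for example Day 127 as in Table 1a for ACQ-6.
- Amend the two sentences saying that every observation can be allocated to a visit, and state whether the pre-dose footnote excludes unscheduled ADA samples in Days 2–98.
- Leave the PK rule unchanged.

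**Cost.** SAP wording, a little reprogramming and one or two small extra rows, with no new data. It revises the item-level windows introduced in Edition 2.0. Unscheduled laboratory values before Day 127 would leave the by-visit summaries but remain in the listings and maximum/minimum displays.
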